3.4 Potential Risks & Benefits

3.4.1 Known Potential Risks

The available evidence suggests that CBD is safe and well-tolerated in human participants. Numerous studies, including several blinded, placebo-controlled trials, have revealed few adverse effects of CBD orally in doses ranging from 10 mg to 1500 mg per day; there have been no reported effects on blood pressure, heart rate, or respiratory rate, no negative mood effects, and no psychomotor slowing. Commonly reported treatment-emergent adverse events in Phase 3 trials of CBD for Lennox-Gastaut or Dravet Syndrome included diarrhea, somnolence, pyrexia, decreased appetite, vomiting, fatigue, lethargy, and convulsion. All participants in these trials were on concomitant anti-seizure medications. CBD is not noticeably psychoactive.

3.4.2 Known Potential Benefits

Participants may or may not experience clinical benefit from this study. Pre-existing clinical data suggest a possibility that the study drug could produce anxiolytic and anti-addictive effects. Aspects of study participation likely to be beneficial include free medical and psychiatric evaluations, and the attention and support of participating in a clinical trial.

4 Objectives and Purpose

4.1 Primary Objective

The primary objective of this study is to assess circulating cannabinoid levels and safety of CBD administered to patients with AUD at doses calculated to yield circulating CBD levels comparable to those that produced clinically relevant effects in animal models of AUD. We predict that within-group circulating CBD levels will stabilize within one week (i.e. pre-CBD dosing levels obtained after 1 week of treatment will not differ from those obtained after 4 weeks of treatment at each dose), that circulating CBD levels obtained at the 1200 mg/day dose will be comparable to those associated with anti-addictive effects in animal models, (i.e., in the range of 200-400 ng/ml), and that no clinically significant cognitive or motoric impairments, CBD-related serious adverse events, or persisting adverse effects will be observed.

4.2 Secondary Objectives

A secondary objective of this study is to contrast the effects of CBD to those of placebo on several physiological and psychological domains relevant to AUD. Relative to placebo, we predict that CBD will improve self-report measures of craving, anxiety, mood, and self-efficacy, and attenuate stress- and alcohol cue-induced craving and physiological stress response.

The final exploratory objective of this study is to assess the impact of CBD on drinking behavior. Relative to the placebo-treated group, we predict that CBD-treated participants will have fewer heavy drinking days during and for four weeks after treatment with 1200mg/day CBD vs. placebo.

CONFIDENTIAL

This material is the property of the NYU School of Medicine and Langone Health
Do not disclose or use except as authorized in writing by the study sponsor

5 Study Design and Endpoints

5.1 Description of Study Design

The proposed study is a phase I/II, single-center, double-blind, randomized proof-of-concept study designed to assess feasibility and contrast effects of CBD treatment to those of placebo on drinking-related outcomes in patients with alcohol use disorder (AUD). We will evaluate the safety of an extended daily CBD treatment regimen in an AUD population, assess the impact of CBD on neuropsychological and neurophysiological domains implicated in AUD, and generate preliminary data on the impact of CBD on alcohol consumption. Following screening and baseline assessments, 40 participants will be randomized in 1:1 ratio to receive either placebo or 600mg CBD/day (PO) for 4 weeks, immediately followed by 1200mg CBD/day (PO) for an additional 4 weeks (8 weeks in total). These doses are calculated to achieve the serum CBD levels reported to reduce alcohol-seeking behavior in animal studies.

5.1.1 Primary Study Endpoints

Circulating cannabinoid levels

Circulating levels of CBD, Anandamide, Delta-9 THC, 11-Hydroxy Delta-9 THC and Delta-9 Carboxy THC will be assessed in CBD-treated participants 45 minutes after the initial administration (T1, T4), 1 day (T2, T5), 1 week (T3, T6), and 4 weeks (T4, T7) of treatment with each dose of CBD. Anandamide levels will also be assessed at these timepoints in placebo treated participants. Additionally, circulating levels of CBD and anandamide will be assessed in CBD-treated participants 12 hours after ingestion of the preceding evening dose following 1 week (T3, T6) and 4 weeks (T4, T7) of administration of each dose of CBD. Plasma CBD levels will be determined via High Performance Liquid Chromatography/Tandem Mass Spectrometry (LC-MS/MS) by collaborators at the Nathan Kline Institute.

Safety

Safety will be assessed by collection of adverse events at all visits after treatment is initiated. LFTs will be obtained at screening, as well as weeks 4, 8, and 9 to assess liver function during and after treatment with study medication. Risk of suicidality will be assessed using the Columbia-Suicide Severity Rating Scale (C-SSRS) [111] by a licensed Clinical Psychologist, NP or MD as part of each study visit (except for the 1-day/T2 and 4 weeks+1-day/T5 visits).

Psychomotor and subjective effects of CBD:

Basic motoric and cognitive function will be evaluated throughout treatment with several established field sobriety tests, including a walk-and-turn task, one-leg stand, Romberg's test, finger-finger test, and counting backwards [97]. The Addiction Research Center Inventory (ARCI), 49-item version [98], will be used as a measure of the intoxicating effects and abuse potential of CBD. Breath Alcohol Concentration (BAC) will also be measured to ensure participants are not under the influence of alcohol during administration of these tasks. Between-group differences on psychomotor tasks (T1-T8), cognitive measures (T3, T6) and number of adverse events (T1-T9) will be assessed.

Cognitive Function:

Several established neuropsychiatric and cognitive tasks will be administered to evaluate the impact of CBD vs. placebo treatment on cognitive domains potentially affected by CBD and/or THC. The Rey Auditory Verbal Learning Task (RAVLT) will be used to assess episodic memory [99, 100], the Mental Rotation Task (MRT) will evaluate visuospatial ability [101, 102], a Time Reproduction Task (TRT) will measure encoding and retrieval of time intervals [88], and several WM Span tasks (OSpan, RSpan, SymSpan, RotSpan) will measure working memory capacity [103, 104].

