8.5 Prohibited Medications, Treatments, and Procedures

Treatment with medications including cannabinoids; treatments for addictions including alcohol; moderate to strong inhibitors of CYP3A4 or CYP2C19; medications metabolized primarily by CYP3A4, CYP3A5, or CYP3A7; and medications with a narrow therapeutic index which are substrates of UGT1A9, UGT2B7, CYP2C8, CYP2C9, CYP2C19, CYP1A2, or CYP2B6 will not be permitted unless discussed with and approved by the PI.

9 Definitions of Key Terms

An adverse event (AE; also referred to as an adverse experience) is any untoward medical occurrence associated with the use of a drug (pharmaceutical investigational product) in humans, which does not necessarily have a causal relationship with that treatment. An AE can therefore be any unfavorable and unintended sign (e.g., an abnormal laboratory finding or test result), symptom, disease, accident, or worsening (increase in severity or frequency) of a pre-existing abnormality, temporally associated with the use of the drug, whether or not considered related to the drug. An AE can arise from any use of the drug (e.g., off-label use, use in combination with another drug and from any route of administration, formulation, or dose, including overdose).

A serious adverse event (SAE) is an adverse drug or biologic or device experience occurring during any study phase (i.e., screening, admission, treatment, or follow-up), and at any dose of the study drug, comparator or placebo, that results in one or more of the following criteria:

- Results in death
- Is life-threatening*
- Requires in-patient hospitalization (i.e., admission) or prolongation of existing hospitalization

CONFIDENTIAL

This material is the property of the NYU School of Medicine and Langone Health
Do not disclose or use except as authorized in writing by the study sponsor

- Results in persistent or significant disability** or incapacity
- Is a congenital abnormality or birth defect (in an offspring)

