11.4 Specific guidelines for assessing laboratory values as adverse events

Any laboratory abnormality, including leukopenia, absolute neutropenia, or thrombocytopenia, will not be considered an AE unless this abnormal laboratory value results in clinical sequelae, such as infection, bleeding, or an intervention. If an abnormal laboratory value results in a clinical event, then the clinical event, not the abnormal laboratory value, must be recorded as an AE. The clinical event must be reviewed to determine if it meets the criteria for an SAE.

12 Assessment of Adverse Events

The following definitions, developed in accordance with the US Code of Federal Regulations (CFR) and the International Committee on Harmonization (ICH), will be used for the purpose of identifying AEs in this clinical study.

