12.2 Severity

The determination of severity must be made with the appropriate involvement of a medically qualified investigator. The investigator will evaluate the severity of each AE using the following three terms and definitions:

Minimal: single occurrence that is not distressing and does not limit activities

Mild: multiple occurrences, awareness of sign or symptom but easily tolerated, usually does not require intervention or limit activities

Moderate: discomfort sufficient to cause interference with normal activities; intervention may be needed

Severe: incapacitating, with inability to perform normal activities; treatment or other intervention usually needed

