17.2 Temperature Deviations

In the event that the temperature at which the IP is stored is less than 2°C or greater than 8°C, the CRC and PI will be notified immediately and a temperature deviation form will be completed and sent via email to contacts designated by Tilray as soon as possible. Tilray will provide further guidance on how to proceed on a case-by-case basis.

18 Study Halting Rules

When three severe AEs are determined to be “probably related” to the study agent, the DSMB will be informed and asked to convene in order to determine whether action should be taken. The Principal Investigator will inform the DSMB members within 24 hours of this occurrence and will provide the DSMB with AE listing reports. The DSMB will convene an ad hoc meeting by teleconference or in writing as soon as possible. The DSMB will provide recommendations for proceeding with the study to the Principal Investigator. The Principal Investigator will inform the FDA of the DSMB’s decision and the disposition of the study. If the DSMB finds it is likely that CBD is contributing to negative outcomes, they will consider solutions including protocol changes or potentially stopping the study.

19 Safety Oversight

Medical and Safety Monitoring

The research team (project manager, coordinators, and research assistants) will submit any adverse events to the PI. The PI is responsible for reviewing all AEs and serious adverse events (SAEs) reported. All SAEs will be reviewed at the time they are reported in the electronic data capture system. All AEs will be reviewed on a weekly basis to observe trends or unusual events.

The PI will generate and present reports for Data Safety Monitoring Board (DSMB) meetings. The DSMB will receive listings of AEs and summary reports of all SAEs at a frequency requested by the DSMB, but at least annually. Furthermore, the DSMB will be informed of expedited reports of SAEs.

Data and Safety Monitoring Board (DSMB)

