A Data and Safety Monitoring Board (DSMB) will be established, comprising three individuals appointed by the PI. The members of the DSMB will have the following backgrounds/expertise: one member with expertise in clinical trials for alcohol use disorder, one member with expertise in clinical trials involving pharmacological interventions, one member with expertise in clinical trials for mood disorders, and one member with expertise in clinical trials for anxiety disorders. This committee will meet (in person or by teleconference) prior to enrollment of the first participant, and at least annually thereafter, including meetings following completion of treatment of the first 5 completers, after completion of treatment of the first 20 completers, and upon completion of enrollment for the trial. Prior to each meeting, the PI will prepare a report to the Board including review of:

- Protocol and ICF changes
- Protocol violations and deviations
- Documentation of informed consent
- Enrollment and retention
- Investigator or key personnel changes
- Aggregate analysis of adverse events/serious adverse events
- Protection of confidentiality

Following each meeting, the board will provide the PI with a report including a recommendation to continue the study unchanged, continue with modifications of the protocol and/or the consent form to protect participant safety, or terminate the study.

20 Clinical Monitoring

Site staff will be required to audit source documentation, including informed consent forms and HIPAA forms, regulatory documents and case report forms on a biannual basis. Site staff will be responsible for local quality

CONFIDENTIAL

This material is the property of the NYU School of Medicine and Langone Health
Do not disclose or use except as authorized in writing by the study sponsor

assurance and will verify that study procedures are properly followed and that site staff are trained and able to conduct the protocol appropriately. If the site staff's review of study documentation indicates that additional training of study personnel is needed, this will be arranged as per the PI. Study team members will review each other's data for completeness, accuracy, and fidelity to the protocol.

21 Statistical Considerations

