21.3.2 Analysis of the Primary Endpoint(s)

For Hypothesis 1a, acute circulating levels of CBD will be assessed in CBD-treated participants 45 minutes after initial administration (T1, T4), and 45 minutes after administration of the morning dose of medication following 1 day (T2, T5), 1 week (T3, T6), and 4 weeks (T4, T7) of treatment with each dose of CBD. Additionally, circulating levels of CBD will be assessed in CBD-treated participants 12 hours after ingestion of the preceding evening dose following 1 week (T3, T6) and 4 weeks (T4, T7) of administration of each dose of CBD. Levels of CBD (mean and standard deviation) will be reported at each timepoint and effects of dose and timepoint will be evaluated. For Hypothesis 1b, circulating CBD levels (mean and standard deviation) 45 minutes after administration of the morning dose of medication following 1 week (T3, T6) and 4 weeks (T4, T7) of treatment with each dose of CBD will be reported in CBD-treated participants. For Hypothesis 1c, between-group differences on psychomotor tasks (T1-T8), cognitive measures (T3, T6) and number of adverse events (T1-T9) will be assessed.

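### LFTs are a primary safety measure with no by-arm analysis, and section 11.4 keeps an enzyme rise without sequelae or intervention out of the AE comparison, the DSMB report list and the halting count

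*Combined protocol and SAP*

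**What the plan says.** Section 5.1.1 (Primary Study Endpoints, Safety) names liver function tests next to adverse events: "LFTs will be obtained at screening, as well as weeks 4, 8, and 9 to assess liver function". Section 10 also names safety laboratory values among the safety variables.

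The analysis sections do not return to them. For Hypothesis 1c, section 21.3.2 says that "between-group differences on psychomotor tasks (T1-T8), cognitive measures (T3, T6) and number of adverse events (T1-T9) will be assessed". Section 21.3.4 (Safety Analyses) covers CBD and THC levels, change in 12-hour CBD levels, field sobriety results, collection of AEs and SAEs, and abuse-potential scales.

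Two sections define when a laboratory result is an AE. Section 9: "An AE can therefore be any unfavorable and unintended sign (e.g., an abnormal laboratory finding or test result". Section 11.4: "Any laboratory abnormality, including leukopenia, absolute neutropenia, or thrombocytopenia, will not be considered an AE unless this abnormal laboratory value results in clinical sequelae". Section 11.4 gives infection, bleeding and an intervention as examples of sequelae. If a clinical event does follow, "then the clinical event, not the abnormal laboratory value, must be recorded as an AE".

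Safety oversight runs on AEs. The only safety-outcome item in the section 19 DSMB report list is "Aggregate analysis of adverse events/serious adverse events". Section 18 convenes the DSMB on a count: "When three severe AEs are determined to be" probably related to the study agent. Section 12.2 defines the top grade by function: "Severe: incapacitating, with inability to perform normal activities".

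**The concern.** The study recognises the liver risk: the version 2.7 entry in the amendment log records that raised liver enzymes were added to the consent form. The population makes a single raised value hard to read. Entry requires at least 6 heavy drinking days in 30, ALT and AST may be as high as 2.5 x ULN under section 6.2, and nothing requires abstinence during treatment. A rise in one participant may come from alcohol or from drug, and the comparison with placebo is the main means of telling them apart.

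Hypothesis 1c predicts no CBD-related serious events and no persisting adverse effects. As the plan stands, it could be reported as supported on AE numbers while a difference in enzymes between arms, including one still present at week 9, had no place in the planned comparison. The gap is in the between-arm safety evidence, not in the care of individuals.

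**Working it through.** The plan states no figure on this point, so there is none to reproduce. The check is mainly of text.

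**1. Trace a rise in ALT or AST that has no sequelae and leads to no intervention.**

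| Place in the plan | What it takes in | Does the rise enter? |
|---|---|---|
| 11.4, AE rule for laboratory values | Abnormality with sequelae or intervention | No |
| 9, general AE definition | Abnormal laboratory finding may be an AE | Possibly; conflicts with 11.4 |
| 21.3.2, Hypothesis 1c | Psychomotor tasks, cognition, number of AEs | No, if 11.4 governs |
| 21.3.4, safety analyses | Cannabinoid levels, sobriety tests, AEs/SAEs, abuse scales | No |
| 19, DSMB report | 7 listed items, one on safety outcomes (AEs/SAEs) | No, if 11.4 governs |
| 18, halting trigger | Three severe, probably related AEs | No |

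Section 11.4 is the specific rule for laboratory values and would normally prevail over the general definition in section 9, but the protocol does not say so. The last row holds even under section 9: a silent rise recorded as an AE could not be graded severe on a scale that requires incapacity.

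**2. Data collected but not used.** LFTs after first dose are due at T4, T7 and T8. With 40 randomized and full attendance, 3 x 40 = 120 panels, 60 per arm, have no stated summary.

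**3. How often it might matter.** The documents give no rate, so the rates below are assumptions. Let p be the chance that a CBD participant has such a rise, with n = 20 per arm (40 randomized 1:1). Expected cases are 20p, and P(at least one) = 1 - (1 - p)^20. At p = 0.10 this is 1 - 0.9^20 = 0.878. P(three or more) is the binomial tail. The last two columns give the power of a two-sided Fisher test at 0.05 if placebo rates were 1% or 5%.

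| p | Expected cases | P(at least 1) | P(3 or more) | Power vs 1% | Power vs 5% |
|---|---|---|---|---|---|
| 0.05 | 1 | 0.642 | 0.075 | 0.002 | 0.002 |
| 0.10 | 2 | 0.878 | 0.323 | 0.036 | 0.017 |
| 0.15 | 3 | 0.961 | 0.595 | 0.143 | 0.070 |
| 0.20 | 4 | 0.988 | 0.794 | 0.317 | 0.168 |
| 0.30 | 6 | 0.999 | 0.965 | 0.690 | 0.446 |

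Under 11.4 the number of these cases recorded as AEs is 0 in every row. That restates the rule and is not an estimate.

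**4. What the table implies.** Cases are likely to occur at modest rates, but a test of proportions would usually miss the difference: power is at most 32% for rates up to 20%. A clean result is also limited. With 0 of 20 cases, the one-sided 95% upper limit is 1 - 0.05^(1/20) = 13.9%. By-arm counts with exact intervals would show both facts; an AE count shows neither.

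**The case against.** The strongest reply is that the plan is not silent on laboratory abnormalities.

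- Section 11.4 has an exception for an intervention, a term the protocol leaves undefined. Reducing or stopping study drug under 7.1.8 could qualify.
- Section 6.6.1 lets the investigator end participation for a laboratory abnormality or a newly met exclusion criterion. ALT or AST above 2.5 x ULN is such a criterion. The reason would then be tallied under 21.3.5, and retention is on the DSMB list.
- Section 6.7 allows suspension for unacceptable risk, 16.3 requires reporting of unanticipated problems, and 16.1 requires that the manufacturer be told promptly of significant safety issues.
- The DSMB is not confined to its listed items. The version 3.0 log entry shows it reviewing ketoacidosis in Type I diabetes, with a new exclusion as the result.
- Section 21.1 promises a formal SAP, which could add an LFT table.

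All of this stands. A reader might infer that 11.4 bars every symptom-free rise from being an AE, or that a liver signal could reach nobody. The documents do not support either reading, because of the intervention exception, section 9 and the routes above.

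What the reply does not supply is a by-arm view of the liver tests. The withdrawal routes are discretionary, and the tally has no stated comparison between arms. Section 7.1.9 also limits the primary statistical analyses to those who complete through T7, so a participant withdrawn earlier for a liver reason would leave them. A SAP can add a table, but the AE count and the section 18 trigger follow the protocol's own definitions.

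**Conclusion.** The point holds for a liver-enzyme rise with neither clinical sequelae nor an intervention. On the protocol's text, such a rise is in no planned between-arm comparison, in none of the 7 listed DSMB report items, and outside the only halting count. It can surface only indirectly.

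This rests on 11.4 prevailing over section 9. If section 9 prevailed, the rise could be counted as an AE, but the plan would still have no LFT summary and the severity scale would still keep it out of the halting count. No planned analysis means none in the documents reviewed, since the formal SAP is still to come.

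The size cannot be fixed from the documents. At assumed rates of 5% to 20% on CBD, 1 to 4 cases would be expected among 20. A reader might infer that the plan forgoes a test that would have found a liver effect. The power figures do not support that: what is lost is descriptive evidence and a prompt for DSMB review. The correction should be made, because the risk is one the study has already told participants about.

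**What to change.** 1. Reconcile 11.4 with section 9, so that clinically significant LFT elevations are recorded as AEs with or without symptoms. The sponsor should set the threshold. Grade these events by multiples of ULN, not by the functional terms in 12.2.
2. In 21.3.4, add a descriptive by-arm table of ALT, AST, Alk Phos and bilirubin at T0, T4, T7 and T8. Include all dosed participants, with those withdrawn before T7. Give counts above set multiples of ULN with exact 95% confidence intervals. No significance test or mixed model is needed at 20 per arm.
3. Add by-arm LFT summaries to the DSMB report list in section 19, and a liver threshold that prompts DSMB review to section 18.

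The cost is wording in 11.4, 18, 19 and 21.3.4, one extra table, and some additional recorded AEs, probably in both arms. The blood is already drawn at all four visits, so there are no new tests or visits. As a protocol amendment, the change needs IRB approval under section 24.2.
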